Project Title: A pilot study of prostate cancer-specific anxiety in active surveillance

Name of Principal Investigator: [name]

Name of Sub-investigator(s): [name]; [name]; [name]; [name]

Name of Biostatistician: [name];

Name of Research Coordinator: [name], MS

Name of Research Analyst: [name]

Protocol version and date: Version 1, February 24, 2017

I RESEARCH OBJECTIVES AND PURPOSE OF THE STUDY

The purpose of this study is to identify patients undergoing active holistic surveillance (AHS) for prostate cancer who have anxiety associated with their diagnosis, to implement a 12-week licensed psychologist-facilitated group intervention in this patient population to determine if treating disease-related anxiety improves quality of life, delays radical, elective treatment of prostate cancer, and to monitor symptom progression and remission during and after therapy.

Our goal is to further our understanding of anxiety in men who are diagnosed with prostate cancer, and to determine if effectively treating disease-related anxiety can improve patients' quality of life, delay radical, elective treatment, and potentially improve disease progression.

II BACKGROUND AND RATIONALE

Previous research suggests that the prevalence of anxiety in prostate cancer (PCa) patients undergoing active surveillance (AS) may be two to three times greater than anxiety levels of similarly aged men in the general population who have not been diagnosed with prostate cancer¹. There is concern that substantial feelings of anxiety in men undergoing AS may be enough to divert PCa patients from AS to pursue definitive treatment².

To date, there is no consensus with regard to the optimal active surveillance protocol. Most active surveillance regimens consist of regular prostate-specific antigen (PSA) tests, digital rectal exams (DREs), and serial biopsies to assess for signs of progression.

Although numerous studies have assessed the psychological impact active surveillance may have on men, no study has examined the role that a holistic regimen may have on these men's health-related quality of life (HRQoL). The aim of this study is to determine the extent to which disease-related anxiety in patients undergoing our institution's AS protocol may alter their course of treatment. It is possible that the psychosocial concern of living with cancer may have adverse effects on PCa patients, and the anxiety related to living with cancer may be enough to divert PCa patients from participating in AS to pursue definitive treatment². Previously, it has

been demonstrated that, at the moment of treatment choice, fear of disease progression is the main reason patients reject AS for a more radical treatment approach⁴.

Clinical studies have investigated the claim that men who choose AS as a treatment option may be at higher risk of psychological distress than men who choose a more radical approach¹. Patients with PCa undergoing AS experienced substantially higher rates of depression and anxiety, when compared to a control population¹. This may be due in part to the passive nature of AS, but studies have also shown that the adverse side effects of PCa may also contribute to an increase in anxiety and depression levels for men undergoing AS¹.

Some data suggest PCa patients undergoing AS may benefit from psychological interventions such as behavioral therapy, group therapy, or mindfulness-based stress reduction⁵. In one study, AS PCa patients who participated in a mindfulness training program for 8-weeks demonstrated significant decrease in PCa-related anxiety. These patients also reported significant increases in global mental health, posttraumatic growth, and mindfulness⁵. Other studies have yielded similar results, demonstrating that educating patients about PCa and how to manage the adverse side effects through cognitive-behavioral interventions may also reduce disease-related anxiety in patients undergoing AS³.

III STUDY DESIGN

Patients who are diagnosed with PCa will be given the Memorial Anxiety Scale for Prostate Cancer (MAX-PC) which is a highly internally consistent, and concurrently and discriminately valid questionnaire used to identify levels of anxiety related to prostate cancer^{6,7} as well as the Generalized Anxiety Disorder-7 (GAD-7) scale, which is a valid, reliable, and efficient 7 item scale used to identify patients with generalized anxiety disorder and has also been effectively used in a population of men with prostate cancer^{8,9}.

Those PCa patients who have elected AS, obtain a score of ≥ 16 on the MAX-PC, and who meet other inclusion criteria, will be randomly assigned to the treatment or control group. Patients assigned to the treatment group will receive 12 weekly 1-hour sessions of structured group therapy intervention led by a licensed psychologist, in addition to AS educational material. Patients assigned to the control group will receive the standard AS educational material only. The research coordinator, who will be responsible for disseminating the educational material and answering patient questions regarding AS, will be blinded to the randomization outcome the the study subjects.

Patients in both the treatment group and control group will be monitored using MAX-PC, GAD-7, and Functional Assessment of Cancer Therapy-Prostate (FACT-P) questionnaires at various time points, as described below. We hypothesize that those patients who undergo group therapy will have a significant reduction in their disease-related anxiety, as reflected by a reduction in their MAX-PC score by the end of their 12-week group therapy intervention. Furthermore, we expect to see an improvement in their quality of life, as measured by the scores obtained on the FACT-P. In addition, results of the program intervention will be correlated with PSA level changes.

Interventions

- 12 1-hour group therapy sessions, occurring once a week
- Facilitated by licensed psychologist
- Group therapy will be conducted using a manualized CBT treatment for anxiety, modified to focus on disease-related anxiety, and incorporating mindfulness-based stress reduction exercises.
- Participants will complete the MAX-PC, GAD, and FACT-P during the 4th and 12th weeks of therapy. Those who are absent during the 4th week and/or 12th week will be given the questionnaires to fill out during the next session or within 7 days.
- Any participant in the study who presents with suicidal/homicidal ideations will be assessed for suicidality/homicidality and referred to Winthrop-University Hospital's ED for treatment if he is deemed to be at imminent risk of harm to himself or others.
- Participants will be asked to consult with the psychologist or treating physician before taking psychotropic medications as they may affect the results of the study.

IV RESEARCH METHODS

1. Method of Subject Identification and Recruitment. Subjects will be identified by their physicians based on their primary diagnosis of prostate cancer. No advertising or outside recruitment will be employed.
2. Process of Consent. Physicians treating the patient for prostate cancer at WUH will be responsible for obtaining consent from potential participants. The consent form and the process will be fully explained, and patients will have a chance to review the form before signing. This will allow the process to be conducive to rational and thoughtful decision making by the subject or the subject's legally authorized representative.

The following details are directly from the Institutional Review Board policies at WUH and slightly edited to fit the format of this research: The individual who signs the informed consent form as the "person obtaining consent" is responsible for conducting the entire consent process. This means:

- a. All aspects of the study, as described in the informed consent form, are first discussed with the potential participant.
- b. The informed consent form is thoroughly reviewed with the potential participant answers to the potential participant's questions are provided.
- c. While reviewing the informed consent form, the person obtaining consent asks questions designed to assess the potential participant's understanding of the material. The person will specifically state this intent to the potential participant (i.e., the person is making sure the potential participant appreciates what the participant is being asked to do, and why).
- d. The potential participant is given ample opportunity to decide, without coercion or undue influence, whether or not the participant wants to be in the study.
- e. The consent process does not end with the formal signing of the consent document. Rather, it is an ongoing process that continues throughout the participant's participation in the research study. The Principal Investigator is responsible for continued assessments of the participant's understanding of what

is happening to the participant, his/her willingness to continue participating and for providing the participant with any new information that may affect the willingness to participate.

3. Subject Capacity. All subjects to be included in this study must possess the capacity to sign a consent form independently.
4. Subject/Representative Comprehension. The investigator is responsible for ensuring that the subject participating in this research is fully aware of the nature of the study.
5. Debriefing Procedures. No debriefing procedures are deemed necessary in support of this research.
6. Consent Forms. A consent form must be signed by every subject participating in this study.
7. Documentation of Consent. The Principal Investigator is responsible for ensuring that valid consent is obtained and documented for all subjects.
8. Costs to the Subject. There are no foreseen additional costs to the patients who choose to participate in this research aside from the time that it takes to complete the questionnaires.
9. Payment for Participation. There will be no payment offered as compensation for participation in this study.
10. Data Analysis and Data Monitoring. We will compare the baseline and outcome MAX-PC and FACT-P scores by the end of the group therapy intervention (week 12). Monitoring and reporting unanticipated problems will be handled by the lead investigator and/or the head of the Urology Department. If a patient wishes to be withdrawn from the study, they may opt out at any time. Considering the minimal invasiveness of our approach, we predict this situation to be unlikely.
11. Data Storage and Confidentiality. Subjects' names and any personal identifying data will be excluded from any public access and protected based on the privacy standards at WUH. Data will be stored in a secure computer in the office of the lead investigator, [name]. Access to this information will only be allowed to authorized investigators participating in the study. There is no expected expiration date to this study as it is intended to be an ongoing database.

V SUBJECT SELECTION AND STUDY ENTRY

1. Number of subjects: 48
2. Gender of Subjects: All subjects to be included in this study will be male.
3. Age of Subjects: The subjects of this study will be over the age of 40.
4. Racial and Ethnic Origin: No discrimination will be made based on race or ethnic origin of subjects.

5. Inclusion Criteria: Inclusion requirements for this study are men above the age of 40 with a primary diagnosis of Prostate Cancer, and initial MAX-PC score of ≥ 16 . In order to participate, patients must sign a consent form allowing related information to be included in this research. This form will be written in simple terms clearly stating the voluntary nature of their participation.
6. Exclusion Criteria: Subjects will be excluded from the study if prostate cancer is not their primary diagnosis. Subjects who, in the judgment of the investigator, cannot appropriately fill out the questionnaires will also be excluded from the study. Subjects will be excluded if they have pre-existing diagnosed psychiatric conditions, are currently taking psychotropic medications (e.g., antidepressants, anxiolytics, mood stabilizers), or have been diagnosed with cancer other than prostate cancer (and non-melanoma skin cancer), and/or evidence of active substance abuse. Participants in the treatment group who are absent from more than 3 therapy sessions will be excluded.
7. Vulnerable Subjects: Elderly subjects being treated for prostate cancer may have diminished decisional capacity. Subjects deemed in the judgment of the investigator to be unable to sign consent will be excluded from the study.

VI RISKS AND BENEFITS

1. The risks to the patient are:
 - a. The potential for unforeseen exposure of information and breach of confidentiality.
 - b. The possibility that a patient may feel uncomfortable answering certain questions regarding sexual and urinary function.
2. Protection against Risks.
 - a. In order to protect private patient information and confidentiality, the data will be password protected and encrypted.
 - b. If a subject feels uncomfortable with answering questions, they will be allowed to opt out of responding to those questions.
3. Potential Benefits to the Subjects. Potential benefits include patient treatment for anxiety and therefore possible quality of life improvement.

VII STATISTICAL ANALYSIS

Statistical methods: The investigators will perform all data analysis. Two groups, the experimental (recipients of group therapy) and the control (literature only) will be compared for anxiety based on their MAX-PC and FACT-P questionnaire scores. PSA anxiety scores will be summarized via descriptive statistics (mean, median, standard deviation, range) at baseline, 4 weeks, and 12 weeks for each treatment arm. Average pre/post changes (12 weeks – baseline) will also be computed for each treatment arm, along with 95% confidence intervals. Analysis of covariance will be used to examine our primary hypothesis that 12-week anxiety scores will be lower in patients receiving group therapy by regressing 12-week PSA anxiety scores onto baseline PSA scores and an indicator variable for treatment arm (12 weeks of group therapy vs.

standard follow-up). The estimate, 95% confidence interval and statistical significance of the treatment effect are the main statistics of interest. In secondary analysis, a mixed effects model will be used when the outcome vector consists of all three measurements (baseline, 4 and 12 weeks) and via statistical contrasts will examine whether the relationship between PSA anxiety scores and time is linear or if the effect of intervention on anxiety scores is fully observed by week 4. Two-sided p-values ≤ 0.05 will be considered statistically significant. All analyses will be conducted using SAS/STAT version 9.4 (SAS Institute, Cary, NC).

Power and Sample size: Power and sample size will be computed via simulation. Normally distributed anxiety scores were assumed such that pre-intervention scores are distributed with mean of 18 (SD=4.0); post-intervention (at 12 weeks) distributed with a mean of 14 (SD=4.0) for a 20% reduction. Pre/post score correlation (ρ) was assumed to be 0.40. The final analysis set in each simulated data set consisted of n patients with baseline (score ≥ 16) and 12-week PSA anxiety score data, where n corresponds to the specified sample size per arm. **A total of n=48 patients will be recruited for the study, for a total of 24 in each study arm.**

Assuming an attrition rate of 25% (n=18 per treatment arm at 12 weeks for analysis), we will have >85% power at the 0.05 level of significance to detect a 20% reduction in PSA anxiety scores from baseline.

VIII ANTICIPATED RESULTS AND POTENTIAL PITFALLS

We anticipate that our study will reveal important characteristics of patients with the diagnosis of prostate cancer, and test a CBT therapeutic approach to reducing the anxiety in these patients. We predict that an anxiety reduction in prostate cancer patients undergoing AHS will improve quality of life, delay radical, elective treatment, and potentially improve disease progression.

We have carefully designed our study so as to minimize the potential for pitfalls. For example, based on the current literature and our clinical experience, the chosen MAX-PC cutoff of 16 will identify a sufficient number of patients from our AHS cohort to enroll in group therapy. In an ongoing study, approximately 50% of our AHS patients exhibited a MAX-PC score of 16+. The risk of patient attrition due to lack of interest in the group-therapy intervention remains, but because we are fully implementing the group therapy into the AHS protocol, we anticipate that the attrition rate will be low, as this has been our experience in our ongoing AHS cohort.

We do not foresee any potential pitfalls that would alter or increase the risk level of the study subjects. The appropriate confidentiality safeguards are already implemented.

References Cited

¹Watts, S., Leydon, G., Eyles, C., Moore, C. M., Richardson, A., Birch, B., ... & Lewith, G. (2015). A quantitative analysis of the prevalence of clinical depression and anxiety in patients with prostate cancer undergoing active surveillance. *BMJ open*, 5(5), e006674.

²Tan, H. J., Marks, L. S., Hoyt, M. A., Kwan, L., Filson, C. P., Macairan, M., ... & Stanton, A. L. (2016). The Relationship between Intolerance of Uncertainty and Anxiety in Men on Active Surveillance for Prostate Cancer. *The Journal of urology*, 195(6), 1724-1730.

³Berg, C. J., Habibian, D. J., Katz, A. E., Kosinski, K. E., Corcoran, A. T., & Fontes, A. S. (2016). Active Holistic Surveillance: The Nutritional Aspect of Delayed Intervention in Prostate Cancer. *Journal of Nutrition and Metabolism*, 2016.

⁴van den Bergh, R. C., Korfage, I. J., & Bangma, C. H. (2012). Psychological aspects of active surveillance. *Current opinion in urology*, 22(3), 237-242.

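### Section IV.10 promises a baseline-to-week-12 FACT-P comparison, but section III schedules FACT-P only in weeks 4 and 12 of therapy and gives it no baseline

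*Protocol*

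**What the plan says.** **Entry.** Section III of the protocol opens with the questionnaires used to find eligible men: "Patients who are diagnosed with PCa will be given the Memorial Anxiety Scale for Prostate Cancer (MAX-PC"), "as well as the Generalized Anxiety Disorder-7 (GAD-7) scale". FACT-P is not named at this step. Randomisation follows.

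**Follow-up.** FACT-P first appears after the randomisation paragraph, as one of three instruments used to monitor both arms: "questionnaires at various time points, as described below". The only times then given are in a bullet under Interventions: "Participants will complete the MAX-PC, GAD, and FACT-P during the 4th and 12th weeks of therapy". The same bullet provides for men who miss those weeks by reference to the next session or a 7-day window.

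**What FACT-P is for.** Section III states the quality-of-life hypothesis: "we expect to see an improvement in their quality of life, as measured by the scores obtained on the FACT-P". Section IV.10 states the comparison: "We will compare the baseline and outcome MAX-PC and FACT-P scores by the end of the group therapy intervention (week 12"). Section VII adds that the two arms "will be compared for anxiety based on their MAX-PC and FACT-P questionnaire scores".

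**Times in the statistical section.** Section VII lists measurements "at baseline, 4 weeks, and 12 weeks for each treatment arm", but for the anxiety scores. It gives no times for FACT-P.

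**The concern.** MAX-PC and GAD-7 have a baseline because they are given at screening. FACT-P does not, yet section IV.10 relies on one. If staff work from section III, the first FACT-P is completed about four weeks into therapy.

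Quality of life is named in the study purpose (section I), and FACT-P is the only instrument assigned to it. A score not taken before randomisation cannot be obtained later, and no analysis plan can supply it. At stake are the change from baseline in each arm and the precision gained by adjusting the between-arm comparison for baseline FACT-P.

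**Working it through.** **Step 1. Trace FACT-P through the protocol.**

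| Place | MAX-PC | GAD-7 | FACT-P |
|---|---|---|---|
| Section III, entry | given | given | not named |
| Section III, Interventions bullet | weeks 4, 12 | weeks 4, 12 | weeks 4, 12 |
| Section IV.10, comparison promised | baseline vs week 12 | not named | baseline vs week 12 |
| Section VII, times listed | baseline, 4, 12 (as anxiety scores) | not named separately | none |

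FACT-P is the only instrument with a promised baseline comparison and no baseline administration anywhere.

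**Step 2. Can week 4 serve as baseline?** No. By then men in the therapy arm have attended sessions, so the score is post-treatment. Section VII treats week 4 in that way for anxiety: its secondary analysis asks whether the intervention effect is already complete at that visit. Adjusting for a score that treatment may have changed would remove part of the effect being estimated.

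**Step 3. Is the control arm covered?** Section III says that both arms are monitored. The only bullet with times, however, sits under Interventions and counts weeks of therapy and sessions, which control men do not have. Their FACT-P timing has to be inferred.

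**Step 4. What is lost and what remains.**
- Lost: change from baseline in FACT-P within each arm, and any analysis adjusted for baseline FACT-P.
- Kept: the unadjusted week-12 comparison between randomised arms, which needs no baseline to be unbiased.

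**Step 5. Size of the precision loss.** The protocol gives no mean, SD or correlation for FACT-P, so FACT-P power cannot be computed. The relative width of the interval for the arm difference, unadjusted to baseline-adjusted, depends approximately only on the pre/post correlation r:

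width ratio = 1 / sqrt(1 − r²)

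- r = 0.40 (section VII's assumption for anxiety, borrowed here): 1 / sqrt(1 − 0.16) = 1 / 0.917 = 1.09, about 9% wider. Equivalently, 18 men per arm without the covariate give the precision of 18 × 0.84 = 15.1 per arm with it.
- r = 0.6 (my assumption): 1 / sqrt(0.64) = 1.25.
- r = 0.7 (my assumption): 1 / sqrt(0.51) = 1.40.

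Only the first rests on a value found in the protocol, and there it refers to another instrument.

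**Step 6. The protocol's own power figure.** Section VII claims more than 85% power with 18 per arm (24 × 0.75 = 18) for the anxiety ANCOVA. With means of 14 and 18 (control held at 18), SD 4.0 and r = 0.40, simulation gives 87.9%, or 87.5% with baseline truncated at 16. The claim reproduces for that 4-point difference. For exactly 20% (3.6 points) the simulated figure is about 80%, which is a separate matter. Neither calculation uses FACT-P.

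**The case against.** **A baseline was plainly intended.** Section IV.10 is current text by the same investigators and presupposes a baseline FACT-P. The Interventions bullet is not a complete schedule: it also omits the baseline for MAX-PC, which certainly exists. The entry paragraph does not claim to list everything done before the first session. This stands as far as intent goes. It makes the problem an omission to be reconciled, and it does not show a decision to skip the measurement. It does not close the gap, because section IV.10 is an analysis statement and tells no one to administer the form.

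**The outcome is not primary.** This stands. The primary hypothesis concerns 12-week anxiety, and FACT-P carries no power claim.

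**Stronger readings that the protocol does not support.**
- A reader might infer that no quality-of-life benefit could be shown at all. Randomisation makes the week-12 between-arm comparison valid without a baseline. Only improvement in the sense of change from baseline is lost.
- A reader might infer that a chance baseline imbalance would go unaccounted for. With 18 per arm its standard error is sqrt(2/18) = 0.33 SD, so a 95% range is 1.96 × 0.33 = ±0.65 SD. This is ordinary sampling variation, and only about r times it carries to week 12 (0.40 × 0.65 = 0.26 SD). The unadjusted interval already allows for it. Quoting it beside the 9% counts one loss twice. Baseline MAX-PC and GAD-7 could also recover some precision, so far as they correlate with FACT-P.
- A reader might take a 25% to 40% widening as the expected size. That needs correlations of 0.6 to 0.7, which appear nowhere in the protocol.

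**Conclusion.** The inconsistency is real and the protocol is wrong as written: section IV.10 relies on a baseline FACT-P that section III does not schedule. If section III is followed, change-from-baseline and baseline-adjusted FACT-P analyses cannot be done.

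The size is moderate. The remaining week-12 comparison would be valid, with an interval about 9% wider on the assumption that FACT-P shares the 0.40 correlation assumed for anxiety. At higher correlations the loss would be larger, but the true value for FACT-P is unknown. The point concerns a non-primary outcome; the primary MAX-PC analysis, its power and the sample size of 48 are untouched. It should be settled before enrolment because the missing score cannot be recovered afterwards.

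**What to change.** Amend section III in three respects:

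1. Every eligible, consented man completes FACT-P with MAX-PC and GAD-7 before randomisation.
2. State the schedule as baseline, week 4 and week 12 for all three instruments in both arms, with control-arm visits counted in a way that does not depend on therapy sessions.
3. Compare week-12 FACT-P between arms adjusted for baseline FACT-P, in line with the ANCOVA already planned for anxiety.

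Section IV.10 then agrees with the schedule. The cost is a short amendment and one more administration of a questionnaire already in use, a few minutes per man at entry. The sample size and the primary analysis do not change.

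### The cost statement omits the 12 weekly sessions and nothing screens for attendance before randomisation, while V.6 excludes poor attenders afterwards, in the therapy arm only

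*Protocol*

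**What the plan says.** - **Cost (Protocol IV.8).** Men who take part are said to face no extra cost "aside from the time that it takes to complete the questionnaires". Time is counted as a cost, and questionnaire time is the only item named.
- **Burden by arm (Protocol III).** "Patients assigned to the treatment group will receive 12 weekly 1-hour sessions of structured group therapy intervention led by a licensed psychologist". The Interventions list repeats it: "12 1-hour group therapy sessions, occurring once a week". For the other arm: "Patients assigned to the control group will receive the standard AS educational material only".
- **Eligibility (Protocol V.5, V.6 and III).** "Inclusion requirements for this study are men above the age of 40 with a primary diagnosis of Prostate Cancer, and initial MAX-PC score" at or above 16, plus signed consent. Section III adds that the man has elected active surveillance. V.6 excludes men for another primary diagnosis, inability to complete the questionnaires, psychiatric history, psychotropic medication, other cancers and substance abuse. None of these concerns ability or willingness to attend.
- **Attendance (Protocol V.6).** The one attendance rule appears among the exclusion criteria: treatment-group men absent from more than three sessions are excluded.
- **Attrition (Protocol VII and VIII).** Section VII plans 24 men per arm and assumes 25% attrition in each, leaving 18 per arm with baseline and 12-week scores. Section VIII says "The risk of patient attrition due to lack of interest in the group-therapy intervention remains", but expects attrition to be low.

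**The concern.** IV.8 is incomplete for the half of the sample allocated to therapy. Their burden is up to twelve hours of sessions, plus any travel, and it comes from the randomised allocation.

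The statistical consequence lies in the order of events. The protocol checks before entry that a man can fill in forms, but not that he can come to a weekly group. Attendance is tested only later, by the V.6 limit, and only men in the therapy arm can fail that test. Absence alone need not lose data, since section III lets men who miss the week 4 or week 12 session complete the questionnaires at the next session or within 7 days. It is V.6 that turns absence into loss.

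If poor attenders differ in their 12-week anxiety from men who attend, the therapy arm as analysed is a selected group compared with unselected controls, and the ANCOVA estimate no longer rests on randomisation. Section VII adjusts for baseline score, which does not remove differences that arise through who stays in therapy.

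**Working it through.** **1. The protocol's own figure.** Inputs from section VII: 24 per arm, 25% attrition, means 18 and 14, SD 4.0, pre/post correlation 0.40, two-sided 0.05.

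- Analysed per arm: 24 × 0.75 = 18.
- Unadjusted power, normal approximation: 4 / (4 × √(2/18)) = 3.00; 3.00 − 1.96 = 1.04; power 85.1%.
- Simulated ANCOVA (20,000 runs, baseline cut at 16, no therapy effect in controls): 88.3%.

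Both agree with the stated figure of more than 85%.

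**2. How many men could pass the V.6 limit.** The protocol gives no attendance rate, so the absence rate q is an assumption, as is independence between sessions. A man is excluded if he misses at least 4 of 12, so P = P(Binomial(12, q) ≥ 4) and the expected number is 24 × P.

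| q per session | P(excluded) | Therapy men of 24 | Controls of 24 |
|---|---|---|---|
| 10% | 0.026 | 0.6 | 0 |
| 15% | 0.092 | 2.2 | 0 |
| 20% | 0.205 | 4.9 | 0 |
| 25% | 0.351 | 8.4 | 0 |

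The control column is zero by construction, because controls have no sessions to miss.

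**3. Effect on power.** Simulated ANCOVA for a 4-point difference, with the inputs of step 1. The loss patterns are assumptions.

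| Therapy / control analysed | Power |
|---|---|
| 18 / 18 (as planned) | about 88% |
| 21 / 18 (screening keeps 3 more therapy men) | about 90.5% |
| 14 / 18 (attendance exclusions on top of 25% attrition) | 83.0% |
| 12 / 18 (same, more exclusions) | 79.1% |
| 12 / 24 (same total of 36, all loss in therapy arm) | 83.5% |

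The power gain from screening is about 90.5 − 88 = 2.5 percentage points.

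**4. Effect on the estimate.** Let a share f of therapy men be lost, and let their 12-week scores have been g points worse than those of stayers with the same baseline. If the stayers' mean is S, the mean of the full arm is (1 − f) × S + f × (S + g) = S + f × g. With no matching loss among controls, the completer estimate is too large by f × g.

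- f = 0.25, g = 2: 0.25 × 2 = 0.5 point.
- f = 0.25, g = 4: 0.25 × 4 = 1.0 point.

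Against the planned 4 points, that is 0.5/4 = 12.5% to 1/4 = 25% of the effect. Both f and g are assumptions. If the lost men would have scored no differently from stayers, the bias is nil. If they would have scored better, it reverses.

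**The case against.** **There is already a filter before randomisation.** IV.2 requires every aspect of the study to be discussed and understanding to be checked, and IV.4 requires that the man be fully aware of its nature. A man who cannot attend may decline then. This stands in part, and it is why one should not say that such men are always discovered only after allocation. But it is an informal filter, and the protocol's own cost statement understates what he is weighing.

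**Group therapy is being built into the surveillance programme (section VIII), so it is not an added cost.** Controls do not receive it, so within the trial it follows from allocation.

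**The real defect is the V.6 rule.** This largely stands. Screening acts upstream of it, and a man who confirms willingness and then misses four sessions is still excluded. A reader might infer that an eligibility criterion would by itself leave no bias and no lost power. It would not.

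**Other stronger readings that the document does not support.**
- That all of the planned 25% attrition is attendance loss. Section VII assumes 25% in each arm, and ordinary withdrawal can occur in both.
- That screening would lift both arms to 21, with power near 92.6%. If attendance loss occurs only in the therapy arm, screening can restore only therapy men.
- That every session is compulsory, or that sessions are at a fixed time. Up to three absences are tolerated, and section III says only that sessions are weekly.
- That the consent form repeats IV.8. It is not among the pages available.

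**Conclusion.** The point holds. IV.8 omits the therapy sessions, no criterion checks ability or willingness to attend before randomisation, and V.6 then builds in a loss that only the therapy arm can suffer.

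Its size cannot be read from the protocol, and section VIII expects attrition to be low. Under the assumed absence rates of 15% to 25%, about 2 to 8 of 24 therapy men would be affected. Selective loss of a quarter of the arm would inflate the estimate by 0.5 to 1 point, if those men would have done 2 to 4 points worse and controls had no matching loss. The gain in power from screening is modest. The main benefit is a less selected therapy arm. This is worth correcting before enrolment because the change is cheap, but screening alone does not settle the problem.

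**What to change.** 1. **IV.8:** state that men allocated to therapy also give the time for twelve weekly one-hour sessions, and travel. Check that the consent form agrees.
2. **V.5, applied before randomisation:** add a criterion such as *confirms he is able and willing to attend the 12 weekly group sessions if allocated to therapy*. Randomise only men who confirm, so that those who cannot attend are left out of both arms alike.
3. **V.6:** state that men who pass the absence limit are still followed to week 12 and analysed in their randomised arm. Without this, the one-sided loss remains for men who confirm and then miss sessions.

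The cost is a corrected sentence, one criterion, a clarified rule, and week 12 questionnaires from men who have stopped attending. Recruitment may be slightly slower, and the results will apply to men willing to attend a group.
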